# 5.4.1. Criteria and procedures for premature discontinuation of treatment or exclusion of a person from research

The study products are administered in a single dose with two syringes on the day of the initial infiltration (regardless of the randomization arm).

Therefore, in principle, there is no reason to discontinue treatment prematurely, except in the event of a reaction (such as an allergic reaction) during the injection, in which case the treatment should be stopped.

If it has not been possible to administer all the products in the patient's randomization arm, this information will be recorded in the CRF. Protocol visits will nevertheless continue.

## 5.4.2. Arrangements for replacing these participants, if necessary

No replacements will be made.

# 6. Treatments administered to research participants

## 6.1. Description of the treatment(s) required to conduct the research

#### 6.1.1. Investigational drug(s)

Treatment identification

#### 1/ Diprostene®:

- INN: Betamethasone

- MA holder: MSD FRANCE

- Dosage form: 1 mL colorless type I glass pre-filled syringe with bromobutyl rubber plunger seal and styrene-butadiene copolymer tip.
- Contains the following excipients: benzyl alcohol, methyl parahydroxybenzoate (E218), propyl parahydroxybenzoate (E216) and sodium.

#### QUALITATIVE AND QUANTITATIVE COMPOSITION

Betamethasone dipropionate	6.43 mg
Corresponding amount of betamethasone	
Betamethasone disodium phosphate	2.63 mg
Corresponding amount of betamethasone	2.00 mg

#### MARKETING AUTHORIZATION NUMBER(S)

320 050-9: 1 ml pre-filled syringe (colorless glass) + 1 sterile needle, 50 mm long and 8/10 mm in diameter + 1 sterile needle 25 mm long and 5/10 mm in diameter

### Indications:

## Systemic use:

Seasonal allergic rhinitis after failure of other therapies (systemic antihistamines, intranasal corticosteroids, or short courses of oral corticosteroids).

#### Local use

These are local corticosteroid therapies when the condition justifies a high local concentration, such as for:

- Rheumatology:
- intra-articular injections: inflammatory arthritis, osteoarthritis flare-up;
- periarticular injections: tendonitis, bursitis;
- soft tissue injections: talalgia, carpal tunnel syndrome, Dupuytren's disease.

## 2/ Sinovial mini®:

- INN: Sodium hyaluronate

- MA holder: Génévrier

- Galenic form: 1 ml pre-filled syringe containing 8 mg HA

- Indication: for infiltration of small joints

- Containing sodium chloride, sodium phosphate and water for injection

# Packaging and labelling

Study products will be packaged and labeled in accordance with current clinical trial regulations, by the Hôtel-Dieu pharmacy at Nantes University Hospital.

Treatment kits will be produced by the Hôtel-Dieu pharmacy at Nantes University Hospital as follows:

- 1st kit: 1 pre-filled syringe of Diprostene (1ml) and 1 pre-filled syringe of Sinovial mini (1ml)
- 2nd kit: 1 syringe of Diprostene (1 ml) and 1 ampoule of 0.9% NaCl (10 ml)

Each kit will be accompanied by instructions for preparation by the IDE.

For the CTC + HA arm: the IDE should keep only 0.5ml of Diprostene from the 1ml syringe and only 0.5ml of Sinovial from the 1ml syringe.

For the CTC and 0.9% NaCl arm: the IDE should keep only 0.5 ml of Diprostene and prepare 0.5 ml of 0.9% NaCl in another syringe.

The nurse preparing the syringes and the doctor performing the procedure will not be blinded.

Syringes will be prepared by the rheumatology department IDE in the operating room.

## Labeling

The treatments under study will be labeled in accordance with good clinical practice and current regulations.

Model label for treatment kits:

Sponsor: CHD Vendée - [name] - [contact]
RHIZ'ART study (CHD046-17)
Diprostene®7mg + Sinovial mini® 8mg KIT
Diprostene®7mg + 0.9% NaCl KIT
Route of administration for injection: intra-articular (refer to protocol)
KIT - center n° - treatment n°
Dispensing date:/
Patient number:Patient name:
Batch no.:Expiry date:/
Store between +4°C and +25°C. Do not refrigerate. Do not freeze.
Drugs for biomedical research only
Use under strict medical supervision

## Treatment manufacturing and distribution:

The CHU Nantes pharmacy will act as the coordinating pharmacy, helping to label and distribute products to pharmacies in the various investigation centers. They will be in charge of supplying study products and will prepare kits (the contents of which are described in paragraph 6.1.1.2) during the preparation campaign.

Regular shipments of these kits will be made to the center pharmacies when the centers open, and during the course of the study, according to the rate of inclusion.

The treatments provided by the sponsor will be made available to the rheumatology department as supplies.

Treatments used in research will be traceable (batch number, expiration date, etc.). Pharmacists at each investigation center will be responsible for:

- Receiving treatment kits
- Storing treatment kits
- Managing and monitoring the provision of treatment kits in the department according to the rate of inclusion

The kits (including preparation instructions) will be given to the designated person in the investigating department. It will be this person's responsibility to prepare the syringes to be administered extemporaneously ("unblinded"), under conditions which ensure that the patient remains blinded, and then to hand them over to the investigating physician, who will administer them under sterile conditions.

A nominative prescription referencing the allocated (blind) treatment number will be written for each patient.

At the end of the study, expired, quarantined or unused syringes may be destroyed with the agreement of the sponsor.

### Administration

#### 1/ Diprostene®:

- infiltration according to GCP of 0.5 ml under ultrasound control
- preparation by the IDE in charge of the study

#### 2/ Sinovial® mini:

- -Infiltration according to GCP of 0.5 ml under ultrasound control
- preparation by the IDE in charge of the study

#### Dosage adjustment

No dosage adjustment is planned since the products are administered in a single infiltration.

Reference documents, leaflets and SmPCs include precautions for use and administration: Sinovial mini®:

Intra-articular injections should only be administered by a doctor. Do not use disinfectants such as quaternary ammonium salts or benzalkonium chloride, as they are known to be incompatible with hyaluronic acid. The possible presence of an air bubble does not compromise the product's

characteristics. The injection site must be located on healthy skin. Inject only into the joint space. Do not inject intravascularly. Do not inject outside the joint line into synovial tissue or the joint capsule. Extra-articular infiltration of Sinovial may cause local adverse effects. Do not use Sinovial in the presence of significant joint effusion. Do not re-sterilize. Syringe and needles are for single use only. To avoid any risk of contamination do not reuse. As with any invasive joint procedure, patients are advised to refrain from physical exertion after the joint injection, and to resume normal activities only after a few days.

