### 4.2.2. Course of the study

### 4.2.2.1. Inclusion

Inclusion and non-inclusion criteria will be verified in a pre-inclusion visit.

On this occasion, the study will be presented to the patient, together with oral and written information and the informed consent form.

During the inclusion visit, the informed consent form and data for the various parameters mentioned above will be collected by means of a clinical examination; an initial ultrasound scan in B mode and Doppler mode, a pain VAS (at rest and during activity), the Cochin scale, grip and opposition strength and a pain VAS during the infiltration procedure.

Two (2) doctors at each center will be investigators and will manage the iterative evaluations. One (1) to two (2) doctors per center will perform the infiltrations; these doctors will not be evaluating doctors.

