### 4.2.2.2. Ultrasound-guided infiltration technique

Infiltrations will be performed on each site in a standardized manner.

The patient is placed in a supine position with arms extended at the side of the body, hands resting on a hard surface, and the palm of the hand to be infiltrated facing upwards.

The reference section is the longitudinal section of the palmar aspect of the joint. The trapeziometacarpal joint is identified as the hypoechoic zone between the 2 bones.

The joint is approached perpendicularly to the probe: the approach is generally lateral to medial but can be easily performed in the other direction depending on the patient's position and the operator's experience. In this technique, the needle appears as a hyperechoic point with a comettail artefact. The needle is introduced perpendicularly to the probe at an angle of 30° to 45° until the hyperechoic spot appears. A 25 G subcutaneous needle is used, with local anesthesia using Xylocaine for the subcutaneous planes and passage of the capsule.

The criterion for success is that the infiltration is performed without resistance, with distension of the capsule observed on ultrasound.

This technique was chosen because it allows intra-articular verification as shown by Di Sante who administered intra-articular injections of hyaluronic acid using a perpendicular approach to the probe, and in 100% of the patients obtained a bulging appearance of the capsule after injection, indicating the intra-articular localization of the product. 

Similarly, in an anatomical study, Umphrey et al demonstrated the intra-articular localization of the infiltration product by arthrography in 17 cadavers, with 16 (94%) actually having had an intra-articular injection. 

Depending on the randomization arm, either 0.5 ml of CTC and 0.5 ml of 0.9% NaCl; or 0.5 ml of CTC and 0.5 ml of HA will be injected.

During these infiltrations, a sterile drape will be placed vertically on an infusion stand, to ensure patient "blinding".

Therefore, the operator will not be blinded; but this doctor will not be the evaluating doctor, who will be effectively blinded to the product(s) injected.

Each infiltration will be followed, if necessary, by a 48-hour work stoppage in accordance with standard practice.

Each patient will be fitted with a resting orthosis for use at night.

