### Study schedule:

Actions	M-1 (Pre-inclusion visit)	M0 (Inclusion visit)	M1	М3	M6	M12
Checking inclusion/non-inclusion criteria	X					
Signing the informed consent		X				
History	X					
Clinical examination		X	X	X	X	X
Randomization		X				
VAS at rest		X	X	X	X	X
VAS for thumb-index grip (during activity)		X	X	X	X	X
VAS for infiltration		X				
Worst Pain Score		X	X	X	X	X
Cochin scale		X	X	X	X	X
Verbal score for overall change			X	X	X	X
Dynamometer (2x3 measurements)		X	X	X	X	X
B-mode and Doppler ultrasound		X		X		
Concomitant treatments (analgesics, NSAIDs)		X	X	X	X	X
Adverse events		X	X	X	X	X

\* Weekly VAS for the first 3 months will be recorded in the patient's diary. The use of new infiltrations, the number of days off work and any progression to a surgical procedure will be recorded during the 12 months of follow-up.

The time allowed for visits at M1 and M3 (primary endpoint) is  $\pm$ 4 days. The time allowed for the other follow-up visits (M6 and M12) is  $\pm$ 4 week.

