### 4.3. Description of measures taken to reduce and avoid bias

## 4.3.1. Drawing of lots

Randomization will be blinded to patient and evaluator, with 2 groups of patients: one group receiving an injection of hyaluronic acid combined with corticosteroids, and the other receiving an injection of corticosteroids and 0.9% NaCl. Randomization will be stratified by center. It will be carried out in a 1:1 ratio and in blocks.

Capture System software will be used for randomization by connecting to the website: https://www.dirc-hugo-online.org/csonline/. A login, password and study number will be issued by a data manager in the Research Promotion Department of La Roche sur Yon Hospital. The following information must be provided:

- First initial of the last name,
- First initial of the first name,
- Month and year of birth,
- Compliance with inclusion and non-inclusion criteria (yes/no),
- Signing of the informed consent (yes/no).

Randomization will be carried out by the investigator once the possibility of inclusion in the study has been confirmed and the patient's informed consent has been signed.

The inclusion number will be assigned automatically during randomization. A confirmation e-mail will be sent to the person who carried out the randomization, as well as to all those concerned.

The randomization list will be drawn up by a statistician from the Research Promotion Department of La Roche sur Yon Hospital. An explanatory guide to randomization will be available online in Capture System.

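### The protocol bars Sinovial when there is significant joint effusion, but nothing requires effusion to be looked for before randomisation, so the precaution can first apply after allocation and in the HA arm only

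*Combined protocol and SAP*

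**What the plan says.** **The precaution.** Section 6.1.1, under Dosage adjustment, lists precautions for Sinovial mini, among them: "Do not use Sinovial in the presence of significant joint effusion". The Diprostene precautions that follow do not mention effusion. The labelled local uses of the steroid include "intra-articular injections: inflammatory arthritis, osteoarthritis flare-up".

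**Eligibility.** The lists in the Summary and in sections 5.1 and 5.2 do not name effusion or any ultrasound finding. The nearest entries in 5.2 are allergy to either product and a general clause for patients whom the investigator judges unable to follow the protocol.

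**Timing.** Section 4.2.2.1 states: "Inclusion and non-inclusion criteria will be verified in a pre-inclusion visit". In the study schedule the row "Checking inclusion/non-inclusion criteria" is marked at M-1 only. Ultrasound and randomisation are both marked at M0. Section 4.1.2 presents the M0 scan as the baseline for a secondary endpoint.

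**Randomisation.** Under section 4.3.1 the investigator randomises "once the possibility of inclusion in the study has been confirmed" and consent is signed. The system asks for a yes/no on compliance with the listed criteria. It does not ask for a scan result.

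**Injection.** Section 6.1.1 specifies for Sinovial mini: "Infiltration according to GCP of 0.5 ml under ultrasound control". Section 4.2.2.2 says of the person injecting: "Therefore, the operator will not be blinded".

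**If a product is not given.** Sections 5.4.1 and 6.3 have this recorded, and under 5.4.1 visits continue. Section 9.7 counts it as a major deviation, so the patient leaves the per-protocol set.

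**The concern.** A patient who is randomised should be fit for either allocation. Here a patient with significant effusion can meet every listed criterion, be entered truthfully as compliant, and be allocated to a product that the protocol says not to use in that joint. The same patient allocated to steroid plus saline raises no such question.

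Two things are at stake. The first is equal eligibility: a baseline feature of the joint would be acted on in one arm only, after allocation, by someone who knows the allocation. The second is the per-protocol analysis, the only sensitivity analysis that section 9.7 names. It could lose patients with effusion from the HA arm while keeping comparable patients in the control arm.

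The protocol handles several steroid precautions differently. Section 6.1.1 warns about diabetes, severe hypertension and hemodialysis for Diprostene, and section 5.2 has a matching non-inclusion criterion for each, applied to both arms before allocation. The effusion precaution for Sinovial has no counterpart there.

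**Working it through.** **1. Can a patient with significant effusion reach allocation under the plan as written?**

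| Step | Where | Does it stop the patient? |
|---|---|---|
| Eligibility check at M-1 | 4.2.2.1, schedule | No: no scan at this visit, effusion not listed |
| Ultrasound at M0 | 4.1.2, schedule | Not necessarily: it may be read before or after randomisation |
| Confirmation of inclusion, compliance yes/no | 4.3.1 | Not by rule: it refers to the listed criteria |
| General clause on inability to follow the protocol | 5.2 | Only if the investigator chooses to use it |
| Ultrasound-guided injection | 4.2.2.2, 6.1.1 | It should stop HA, but after allocation |

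The last row is the only point where the precaution clearly applies, and it applies to one arm.

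**2. Reproduce the planned sample size.** Inputs from section 9.2: baseline mean 6.4, SD 1.3, reductions of 25% and 35%, power 80%, alpha 5%, 132 patients, raised to 150.

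- Difference = 6.4 × (0.35 − 0.25) = 0.64.
- Standardised difference = 0.64 / 1.3 = 0.492.
- A two-sided two-sample t-test at 5% needs 65.74, so 66 per arm: 2 × 66 = 132, as stated. Power at 66 per arm is 80.2%.
- At 75 per arm (150 in total) power is 85.0%.

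The plan does not state sidedness. Two-sided reproduces its figure.

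**3. Bound the effect on power.** The documents give no effusion rate, so the number k of HA patients from whom HA is withheld is hypothetical. Assume that these patients respond as on steroid alone, that nobody else is lost, and that each arm has 75 patients. Then the intention-to-treat difference is 0.64 × (1 − k/75).

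| k | Difference | Power |
|---|---|---|
| 0 | 0.640 | 85.0% |
| 1 | 0.631 | 84.0% |
| 2 | 0.623 | 83.0% |
| 3 | 0.614 | 82.0% |
| 4 | 0.606 | 80.9% |
| 5 | 0.597 | 79.8% |

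Power equals 80% at a withheld share of 6.46%, which is 0.0646 × 75 = 4.8 patients. These are t-test figures. The planned primary model also adjusts for baseline VAS and center, so they are approximate.

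**4. Per-protocol set.** Each patient from whom HA is withheld removes 1/75 = 1.3% of the HA arm and none of the control arm.

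**The case against.** The strongest reply is that the precaution already does its work. It stands in the protocol, it is worded as a prohibition, and the doctor injecting images the joint while doing so. A reader might infer from the missing criterion that patients will be given HA in an effused joint. The documents do not support that: it would require a doctor to disregard an explicit instruction. This part of the reply stands.

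There is also room to act earlier. The scan is among the data collected at the inclusion visit, section 4.3.1 requires inclusion to be confirmed before randomisation, and the general clause in 5.2 could be used to decline the patient. The supplied text does not forbid deferring the injection either. A reader might take the schedule to show that randomisation precedes the scan, but it is a visit grid and the order of its rows proves nothing. All of this is fair. What remains is that these steps are optional and could be applied differently at three centres. Deferral after allocation would still arise in the HA arm only.

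Nor does every label precaution become a criterion: healthy skin at the injection site and progressive cardiovascular disease are not in 5.2 either. Effusion differs because, as the text stands, it bars one allocation and not the other. That is an argument about symmetry between arms more than about safety.

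Finally, a reader might see a conflict with section 6.3, which calls for the complete dose to be given. There is none, because the same section provides for recorded exceptions.

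**Conclusion.** The point holds as a gap in eligibility and sequence. Nothing in the supplied text requires effusion to be assessed before allocation, so the precaution can first be applied after randomisation, unblinded and in the HA arm only, with per-protocol exclusions on that side only.

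Its size is unknown and probably small. Excluding inflammatory rheumatism and infection (5.2) may lower the frequency but does not close the gap. The power table is a bound under full loss of the added effect. It does not show that any patient is affected.

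A reader might infer that the primary result is biased or underpowered. That is not supported: the main analysis is by intention to treat (9.1, 9.7), patients not given a product continue their visits, and it would take about 5 of 75 HA patients to use up the margin gained by enrolling 150 instead of 132.

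The conclusion covers the supplied text only. The product documents and the ultrasound grading, which the protocol places in Appendices 4 to 6, were not available. A leaflet in an appendix would not by itself add a criterion to section 5.2.

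**What to change.** 1. In section 4.2.2.1 and the study schedule, state that the M0 scan is read after consent and before randomisation, and that eligibility is reconfirmed at that point.
2. In section 5.2 and the Summary, add for both arms: significant trapeziometacarpal joint effusion on the M0 ultrasound (Sinovial not to be used, see 6.1.1). Allow deferral and re-screening once the effusion has resolved.
3. Have the sponsor's ultrasound-trained investigators set one definition of significant effusion for all centres. Do not tie it to OMERACT stage II or III unless Appendix 4 grades effusion: section 4.1.2 uses that scale for the appearance of lesions, and the supplied text does not say whether effusion is part of it.

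The cost is a short amendment. No new procedure is needed, because the M0 scan and the compliance field in the randomisation system already exist, and that field would then apply the rule to both arms alike. The downside is that some patients, probably few, are lost or delayed at screening, and that the result will not cover patients with significant effusion. If effusion proved common, the cost to recruitment would be larger, and the inclusion period has already been extended once.

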## Diprostene®:

Rigorous asepsis is essential.

Local injection of corticosteroids can destabilize diabetes and trigger psychosis and severe hypertension.

Caution should be exercised when administering to patients at high risk of infection, particularly hemodialysis patients or prosthesis wearers.

The risk of vasomotor reactions, particularly chest pain, must be taken account of in patients with underlying progressive cardiovascular disease.

Do not inject intratendinously due to a risk of rupture.

Not for I.V. or I.M. administration.

This product is not suitable for inhalation by nebulizer.

## 6.1.2. Non-experimental drug(s)

6.1.2.1. Treatment identification

NA

6.1.2.2. Packaging and labeling

NA

6.1.2.3. Treatment manufacturing and distribution

NA

6.1.2.4. Administration

NA

6.1.2.5. Dosage adjustment

NA

# 6.2. Drugs and treatments authorized and prohibited under the protocol, including rescue medication

#### 6.2.1. Authorized treatments

All treatments useful for the therapeutic management of the patient are authorized. They must be recorded in the CRF.

#### 6.2.2. Unauthorized treatments

Potential interactions with study products.

The risk of interaction between glucocorticoids and other drugs is considered exceptional for local injections in normal circumstances of use. However, anticoagulants/antiplatelets likely to increase the risk of bleeding, and drugs with immunosuppressive potential that increase the risk of infection should be avoided.

(see Diprostene® SmPC and Sinovial® leaflet (Appendices 5 and 6).

#### 6.2.3. Emergency treatment

NA

#### 6.3. Method for monitoring treatment compliance

The complete dose contained in each syringe must be administered in a single injection. If this is not the case, it will be noted along with the reason in the observation book.

#### 6.4. Storage conditions for experimental drugs

#### 6.4.1. Description of pharmacy storage

A specific procedure describing the contents of the kits and their storage conditions will be drawn up by the CHD Vendée pharmacy and sent to the pharmacies of the investigating centers when the first shipment of study products is made. The kits must be stored at a temperature of 4 to 25°C and the products they contain must be protected from light and any source of heat. The storage area should have restricted and secure access. Storage conditions at room temperature must be guaranteed by a temperature monitoring and recording system.

